7.1.6. Body Measurements

Height (cm) will be measured without shoes at Screening.

Body weight (kg) will be measured without shoes, coats, or sweaters.

Body mass index will be calculated as follows:

body weight (kg) \div [height (m)]²

7.1.7. Magnetic Resonance Imaging

MRI evaluations will be performed at Screening for all subjects and at Day 43 for subjects ≥ 50 years of age to assess for ARIA. If ARIA is detected, repeat MRIs will be performed every 3-4 weeks until the ARIA is resolved.

MRIs will be read at an independent central reading laboratory after screening of the first two sentinel subjects for Cohort 1 (age < 50) who will have MRIs performed and read locally.

Sequences will include the following:

- MRI T2-weighted fluid-attenuated inversion recovery (T2/FLAIR) sequence to detect ARIA-E
- MRI gradient recalled echo (GRE) sequence to detect ARIA-H
- Diffusion weighted imaging (DWI) sequence can help differentiate ARIA-E from potential cytotoxic edema as may be noted with an incidental acute to subacute infarct

7.1.8. Electrocardiogram

Throughout the study, subjects will be monitored for changes in cardiac conduction. Single 12-lead ECGs will be collected at designated visits after at least 5 minutes of quiet rest in a supine position.

7.1.9. Laboratory Assessments

All blood collections should be performed in non-fasting conditions.

Clinical laboratory tests include hematology, blood chemistry panel, urinalysis, and coagulation evaluations. The following assessments will be performed for the respective clinical laboratory tests:

 Hematology panel, including red blood cell count, erythrocyte mean corpuscular hemoglobin concentration, erythrocyte mean corpuscular volume, hematocrit, hemoglobin, leukocyte count, and absolute counts of lymphocytes, monocytes, neutrophils, basophils, eosinophils, and platelets.

- Blood chemistry panel, including blood glucose, calcium, albumin, total protein, sodium, potassium, bicarbonate, chloride, magnesium, blood urea nitrogen, creatinine, creatine kinase, alkaline phosphatase, alanine aminotransferase, aspartate aminotransferase, gamma-glutamyltransferase, bilirubin, lipase, lactate dehydrogenase, phosphorus, triglycerides, total cholesterol, high density lipoprotein cholesterol, and low-density lipoprotein cholesterol.
- Urinalysis, including osmolality, creatinine, calcium, sodium, turbidity, color, specific gravity, pH, protein, glucose, ketones, bilirubin, blood, urobilinogen, nitrite, leukocytes, and microscopic particles. Urine should not be first morning void. Microscopic examination will be performed if urinalysis results are abnormal for bacteria, casts, epithelial cells, erythrocytes or leukocytes. Urine should be collected within 1 hour of blood draws for hematology and chemistry panels. Trace protein will be considered positive.
- Coagulation panel, including (INR, PT, PTT and platelets); results within 2 days prior to the LP must be confirmed and determined to be within normal range before LP.

Other laboratory tests include the following:

- Viral serology, HBsAg and HCV tests
- FSH for post-menopausal women only. Post-menopausal status will be confirmed through testing of FSH levels (≥ 40 IU/mL).
- Pregnancy test for non-post-menopausal women only (serum human chorionic gonadotropin at Screening and urinary chorionic gonadotropin thereafter). If a urine pregnancy test is positive, a serum pregnancy test must be obtained.
- Urine drug (amphetamines, methamphetamines, methadone, barbiturates, benzodiazepines, cocaine, opiates, methylenedioxymethamphetamine, phencyclidine, tetrahydrocannabinol), urine cotinine, and serum alcohol screen

7.1.10. Pharmacokinetic Sampling

Serum samples (approximately 5 mL) will be collected at the timepoints indicated in Appendix 1 to assess the serum PK profile of PMN310. On days when a PK sample is to be drawn and vital signs and/or an ECG are to be recorded, the PK sampling should be done shortly after completion of the vital signs and ECG. Details for collection, handling, and shipment of specimens are provided in the Laboratory Manual.

7.1.11. Antidrug Antibodies

Serum samples will be collected to evaluate the levels of ADAs to PMN310 per the schedule in Appendix 1. Details for collection, handling, and shipment of specimens are provided in the Laboratory Manual.

7.1.12. Exploratory Biomarkers

Residual and unused serum and CSF samples will be stored for the measurement of biomarkers at the timepoints outlined in Appendix 1. Retaining surplus samples from scheduled PMN310-101 study draws and lumbar punctures will be done for all subjects consenting to the study to

permit indefinite storage and subsequent use of those samples for biomarker analysis. Only serum and CSF samples may be saved. Samples retained will be coded or de-identified to permit retention of information at the cohort level. Access to the samples or data would be limited to the Sponsor, central laboratory, storage laboratory, and any third-party analysts. It is possible that data could be shared with future collaborators or published. In the event of publication, no data will be linked to specific subjects, all samples would be de-identified.

7.1.13. Lumbar Puncture

CSF samples to measure safety and concentrations of PMN310 will be collected via LP at times specified in Appendix 1. Up to 20 mL of CSF will be collected during each LP.

Details for collection, handling, and shipment of specimens are provided in the Laboratory Manual.

7.1.14. Concomitant Medication Use

All concomitant medications, including over-the-counter medications or herbal therapies taken within 4 weeks before Screening as well as all concomitant medications taken during the study, will be documented.

7.1.15. Adverse Events

All AEs and serious adverse events (SAEs) will be classified and graded as described below. Definition of Adverse Event

Per the International Conference for Harmonization (ICH) E2A (Clinical Safety Data Management: Definitions and Standards for Expedited Reporting E2A), and 21 CFR 312.32 IND Safety Reporting, an AE is defined as:

Any untoward medical occurrence in a patient or clinical investigation subject administered a pharmaceutical product and which does not necessarily have to have a causal relationship with this treatment.

The following information should be considered when determining whether or not to record a test result, medical condition, or other incident on the Adverse Events or Pre-existing Conditions case report form (CRF):

- From the time of informed consent through pre-dose on Day 1, only study protocol
 related AEs should be recorded. A protocol related AE is defined as an untoward
 medical event occurring as a result of a protocol mandated procedure. Otherwise, all
 other clinically significant medical conditions should be recorded in the medical
 history.
- All medical conditions present or ongoing prior to dosing on Day 1 should be recorded as medical history. Changes in medical conditions (including changes in severity, frequency, or character), during the safety reporting period should be recorded as AEs.
- All AEs reported during and postdose on Day 1 through the follow-up visit at Week 12 will be considered treatment-emergent adverse events.

- All AEs (regardless of relationship to study drug) should be recorded from the time of informed consent through the follow-up visit at Week 12 (see Section 7.1.15.6).
 Complications that occur in association with any procedure should be recorded as AEs with assessed severity whether or not the procedure was protocol mandated.
- In general, an abnormal diagnostic or laboratory value should not be recorded as an AE unless it is associated with clinical signs or symptoms (i.e., assessed as clinically significant), requires an intervention, results in an SAE, or results in study termination or interruption/discontinuation of study treatment. When recording an AE resulting from a diagnostic or laboratory abnormality, the medical condition or diagnosis rather than the abnormality itself should be recorded (e.g., record "anemia" rather than "low hemoglobin").

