
Reference Therapy, Dose and Mode of Administration:	Placebo will consist of 100 mL 0.9% NaCl and will be administered as a matching single IV infusion over 60 minutes, followed by a 15 minute 0.9% NaCl flush.			
Duration of Study:	Enrolled subjects are expected to be in the study for approximately 16 weeks including a screening period (up to 4 weeks), an inpatient single dose and observation period (5 days), and a postdose outpatient follow-up period (12 weeks). Subjects may return 5 weeks after completion of the postdose outpatient follow-up period for an optional follow-up visit.			
Criteria for Evaluation:	 Vital signs MRI evaluations will be performed at Screening for all subjects and at Day 43 for subjects ≥ 50 years of age to assess for amyloid-related imaging abnormalities (ARIA). If ARIA is detected, MRIs will be repeated every 3-4 weeks until there is resolution, regardless of whether or not the subject is symptomatic. MRIs will be read at an independent central reading laboratory after screening of the first two sentinel subjects for Cohort 1 (age < 50) who will have MRIs performed and read locally. Sequences will include: MRI T2-weighted fluid-attenuated inversion recovery (T2/FLAIR) sequence to detect amyloid-related imaging abnormalities characterized by vasogenic edema or sulcal effusions (ARIA-E) MRI gradient recalled echo (GRE) sequence to detect amyloid-related imaging abnormalities characterized by parenchymal microhemorrhages or sulcal/leptomeningeal hemosiderin deposits (ARIA-H) Diffusion weighted imaging (DWI) sequence can help differentiate ARIA-E from potential cytotoxic edema as may be noted with an incidental acute to subacute infarct ECGs Laboratory test results Physical examinations Neurologic examinations Neurologic examinations Neurologic examinations AEs/serious adverse events (SAEs) Serum ADA C-SSRS Pharmacokinetic: Serum PMN310 concentrations will be measured throughout the study to characterize standard PK parameters using non-compartmental methods (e.g., C_{max}, T_{max}, AUC_{0-e}, t_{1/2}, Vd, and CL) CSF will be collected for drug concentrations 			

Biomarkers and ADAs

 Serum and CSF samples will be obtained for measurement of biomarkers and serum samples for ADAs

Exploratory

- Incidence and titers of ADAs
- Residual and unused serum and CSF samples will be stored for future use for the measurement of biomarkers

Statistical Methods:

Determination of Sample Size

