2.2. Study Endpoints

2.2.1. Primary Endpoints

• Adverse events (AEs), clinical laboratory tests (clinical chemistry, hematology, urinalysis), physical and neurological examinations, vital signs, and 12-lead ECGs

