6.1. Screening Period (Day -28 to Day -1)

Healthy volunteers will be recruited for this clinical study. Before initiation of screening assessments, the subject must be given a complete explanation of the purpose and procedures occurring during the study. Subsequently, the subject must sign and receive a copy of an Institutional Review Board (IRB)-approved informed consent form (ICF) (Section 11.4). Once informed consent has been obtained, screening assessments will be performed and eligibility of the subject will be determined based on the inclusion and exclusion criteria. Subjects who fail screening may be rescreened following Sponsor approval.

Study assessments are described in Section 7.

The following evaluations will be performed to assess the subject's eligibility for the study:

- Demography and medical history
- Suicidality evaluation: C-SSRS (Baseline Screening version)
- Height
- Complete physical examination
- Neurologic examination
- Vital signs
- Weight
- MRI
- Lumbar x-rays (at investigator's discretion to rule out any contraindication to lumbar puncture)
- 12-lead ECG
- HBsAg and HCV tests

- FSH (post-menopausal women only)
- Pregnancy test (non-post-menopausal women only)
- Urine drug, urine cotinine, and serum alcohol screen
- Clinical laboratory tests:
 - Blood chemistry and hematology
 - Urinalysis
 - Coagulation
- Review of concomitant medications
- AE assessment of protocol related procedures only, to be performed after informed consent is obtained

The Investigator may use clinical judgment when determining the clinical significance of laboratory results throughout the study. The Medical Monitor may, depending on study criteria, be consulted before enrollment of a candidate with abnormal laboratory values.

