7.1.4. Neurological Exam

Neurological examinations will include the following: mental status, level of consciousness, cranial nerve function, sensory function, motor function, and reflexes.

Clinically relevant findings from the neurological examination performed at Screening will be recorded as medical history. Any clinically relevant treatment-emergent new finding on examination will be documented as an AE.

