7.1.15.5. Procedures for Eliciting and Recording Adverse Events

Investigator and study personnel will report all AEs and SAEs whether elicited during subject questioning, or discovered during physical examination, laboratory testing and/or other means and should be recorded on the CRF and/or SAE Report Form, as appropriate.

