#### **8.3** Clinical Laboratory Evaluations

Chemistry, hematology, coagulation, and urine clinical laboratory results will be summarized descriptively for continuous and categorical lab results, as appropriate, by visit for the observed value as well as for the change from baseline value (continuous lab results only).

In addition, laboratory shift summary tables will be provided where normal/abnormal not clinically significant/abnormal clinically significant/not evaluable status is collected on the CRF.

CONFIDENTIAL Page 23 of 32

For each of these lab tests, the shift table will tabulate the number and percentage of subjects that shifted from normal/abnormal not clinically significant/abnormal clinically significant/not evaluable at Baseline to normal/abnormal not clinically significant/abnormal clinically significant/not evaluable at each post-Baseline visit. Percentages will be based on the number of subjects with non-missing status at Baseline and each post-Baseline visit.

Individual laboratory parameters by visit with normal ranges, and abnormal laboratory assessments will be included in by-subject listings.

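### The AE recording rule ties clinical significance to symptoms, so by default new asymptomatic ARIA at Day 43 is not an AE and no planned table counts it

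*Protocol*

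**What the plan says.** Protocol 7.1.15 sets the recording rule for test results: "In general, an abnormal diagnostic or laboratory value should not be recorded as an AE unless it is associated with clinical signs or symptoms". The sentence continues with a gloss and three further routes: "i.e., assessed as clinically significant), requires an intervention, results in an SAE, or results in study termination or interruption/discontinuation of study treatment".

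Other parts of the documents bear on it:

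- Protocol 6.1, on laboratory results: "The Investigator may use clinical judgment when determining the clinical significance of laboratory results throughout the study". No symptom condition is attached.
- Protocol 7.1.4, on neurological findings: "Any clinically relevant treatment-emergent new finding on examination will be documented as an AE". Section 7.1.3 has an equivalent sentence for the physical examination. Section 7.1.7, on MRI, has none.
- Protocol synopsis, Criteria for Evaluation, if ARIA is detected: "MRIs will be repeated every 3-4 weeks until there is resolution, regardless of whether or not the subject is symptomatic".
- Protocol 2.2.1 lists as primary endpoints AEs, clinical laboratory tests, and "physical and neurological examinations, vital signs, and 12-lead ECGs". MRI is not listed.
- Protocol 9.4.1 names MRI, where indicated, among the safety results to be assessed with summary statistics by cohort.
- SAP 8.3: "laboratory shift summary tables will be provided where normal/abnormal not clinically significant/abnormal clinically significant/not evaluable status is collected on the CRF". SAP 8.4 tabulates the same kind of clinical-significance categories for ECGs and adds QTcF threshold counts.
- SAP 8.7 provides by-subject listings for MRI: one for subjects with ARIA and one for all centrally read scans. It provides no table.

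**The concern.** AEs are the first-listed primary endpoint, and the Day 43 MRI is done to look for ARIA. The synopsis expects that some ARIA may be symptom-free and requires follow-up imaging of it. The recording rule nevertheless makes symptoms the ordinary condition for a test result to become an AE. The protocol therefore treats such a finding as important enough to follow to resolution, but does not say whether it is counted.

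Two things are at stake. First, the TEAE tables could show no ARIA at a dose where ARIA was seen, with the cases visible only in a listing. Second, the wording can be read in more than one way. The study may use up to two sites, with two more possible, so the same asymptomatic scan could be recorded as an AE at one site and not at another.

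**Working it through.** The point rests on text, not on a stated figure, so there is no number to reproduce. The check takes one case (new ARIA-E or ARIA-H at Day 43, no symptoms, no treatment needed) through each route in 7.1.15 and then through the planned outputs.

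**Routes to becoming an AE**

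1. Signs or symptoms: not met, by construction. The parenthesis offers no separate route if it merely restates what having symptoms means.
2. Requires an intervention: not met unless a repeat MRI counts as one. The protocol does not say.
3. Results in an SAE: Section 7.1.15.1 defines an SAE as an AE that meets a seriousness criterion. The route is circular for a finding that is not yet an AE.
4. Study termination, or interruption or discontinuation of treatment: the treatment part cannot apply, because the only infusion is on Day 1. Only termination remains.

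The default result is that no AE is recorded. Routes 2 and 4 could still admit individual cases.

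**Would it be counted if recorded?** Yes. Day 43 lies after dosing and before the Week 12 visit, so it meets the treatment-emergent definitions in protocol 7.1.15 and SAP 8.1. Inclusion criterion 9 requires a Screening MRI free of significant abnormality, including prior microhemorrhages, so a Day 43 finding would ordinarily be new.

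**Where else could each finding appear?**

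| Finding, no symptoms | Own primary endpoint? | Planned SAP table outside the AE tables |
|---|---|---|
| Laboratory change | Yes (2.2.1) | Descriptive and shift tables (SAP 8.3) |
| ECG or QTcF change | Yes (2.2.1) | Clinical-significance categories and QTcF thresholds (SAP 8.4) |
| New examination finding, clinically relevant | Yes (2.2.1) | None, but it is an AE under 7.1.3 and 7.1.4 |
| New ARIA | No | None; listing only (SAP 8.7) |

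Only ARIA lacks both a sentence making it an AE and a table of its own. SAP 3.3 reports no departure from the protocol's analyses, yet SAP 8.7 does not deliver the MRI summary that protocol 9.4.1 describes.

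**Denominator.** Eligibility runs from 18 to 65 years, and only older subjects are scanned at Day 43. The documents set no minimum number of such subjects per cohort. With m active subjects scanned out of 6 dosed, m can be anything from 0 to 6. The proportion for one case is 1/m, and if m = 0 nothing can be detected. The age limit itself differs: Section 7.1.7 and Appendix 1 include subjects aged exactly 50, while Section 6.2.2.4 gives older than 50. Those passages need to be reconciled before m is defined.

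**The case against.** The best defence is that the rule is looser than it looks. It opens with a general qualifier and sits in a list of points to consider. The AE definition in the same section has no symptom condition, and Section 7.1.15.5 asks staff to report AEs "discovered during physical examination, laboratory testing and/or other means". The parenthesis can be read the other way round, as saying that the working test is the Investigator's assessment. On that reading an asymptomatic result judged clinically significant is an AE, and there is no conflict with Section 6.1 or the SAP. The rule also speaks of a value, and ARIA (edema, effusion, microhemorrhage) is arguably a condition. Finally, each detected ARIA would appear in the SAP 8.7 listing, and in groups of six a listing is easy to read.

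Much of this stands. A reader might infer that asymptomatic ARIA is definitely excluded from the AE endpoint. The documents support only a default, with wording that admits the opposite reading. A reader might also infer that asymptomatic hepatic or QTcF changes would go unreported. They would not: laboratory tests and ECGs are primary endpoints with their own summaries, and the possible loss is confined to the TEAE tables.

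The defence does not remove the ambiguity. Nothing in the documents says whether asymptomatic ARIA is an AE, and a listing is not the summary by cohort that protocol 9.4.1 describes.

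**Conclusion.** The point holds as a default and an ambiguity, mainly for ARIA. It is a modest improvement in what the first-listed primary endpoint counts, not a flaw that hides safety data.

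Its size cannot be stated as a rate. A reader might take one missed case as 1 of 6, but that treats unscanned subjects as free of ARIA, and the documents fix neither m nor an expected incidence.

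A reader might also infer that the AE-count pause triggers in Section 5.5 would behave differently. The documents do not support that. Under Table 1, a finding with no symptoms, no effect on activity and no intervention fits Grade 1 best, while those triggers need Grade 2 or 3. Section 1.5 cites an external grading scale that is not reproduced, so its effect cannot be judged. Timing points the same way: escalation review needs data through 7 days postdose, whereas Day 43 is 42 days postdose, 42 − 7 = 35 days later. The committee's general determination, and the provision for a pause on important safety concerns at any time, do not depend on AE counts.

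The conclusion assumes that documents not available here do not already settle the matter: the CRF completion guidelines, the committee charter and the three protocol clarification letters cited in SAP 3.1.

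**What to change.** - Protocol 7.1.15: make the two conditions separate. An abnormal result is recorded as an AE if it comes with signs or symptoms, or if the Investigator judges it clinically significant with or without symptoms. The remaining routes stay as they are.
- Protocol 7.1.7: add that any ARIA-E or ARIA-H absent at Screening is recorded as an AE regardless of symptoms. The SAP 8.1 tables then count it without further change.
- SAP 8.7: add a table of ARIA-E and ARIA-H as n/N by dose level and pooled placebo, with N the number of subjects scanned at Day 43. This brings the SAP into line with protocol 9.4.1 and can be done before database lock even if the protocol wording is left alone.
- CRF completion guidelines: carry the same rule, so that sites classify the same finding alike.

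No change to dosing, escalation, stopping or imaging follow-up is proposed. The cost is two sentences in the protocol, one in the guidelines and one small table. The downside is that a few more AEs are recorded, most of them probably mild.

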7.1.15.1. Definition of a Serious Adverse Event

In this study, an SAE is defined as an AE that meets any of the following criteria:

- Results in death
- Is life-threatening: The term life-threatening in the definition of an SAE refers to an event in which the subject was at risk of death at the time of the event. The term life threatening does not refer to an event that, had it occurred in a more severe form, might have caused death.
- Requires hospitalization or a prolongation of an existing hospitalization: In general, hospitalization signifies that the subject has been detained at the hospital or emergency ward for observation or treatment that would not have been appropriate in the physician's office or outpatient setting. Complications that occur during hospitalization are AEs, but not necessarily SAEs. A medical occurrence or complication that prolongs hospitalization is an SAE. When there is doubt as to whether hospitalization occurred or was necessary, the AE should be considered an SAE. Hospitalization for elective treatments of a preexisting condition that did not worsen from its original baseline level is not considered an SAE.
- A persistent or significant incapacity or substantial disruption of the ability to conduct normal life functions: This does not include AEs of relatively minor medical significance such as uncomplicated headache, nausea, vomiting, diarrhea, influenza and accidental trauma (e.g., sprained ankle) that may interfere or prevent everyday life functions but do not constitute a substantial disruption.
- A congenital anomaly or birth defect
- Other important medical event: Medical or scientific judgment should be exercised when deciding whether reporting is appropriate for other important medical events that may not result in death, be life-threatening, or require hospitalization but still may jeopardize the subject or may require medical intervention to prevent one of the outcomes listed in this definition. These events should also be considered serious. Examples of such events are intensive treatment in an emergency room or at home for allergic bronchospasm, blood dyscrasias, or convulsions that do not result in hospitalization or in the development of drug dependency or drug abuse.

PMN310 Confidential An SAE requires additional detailed reports and follow-up (see Section 7.1.15.8). The content of these detailed reports must address the Investigator's estimate of causality. The Medical Monitor will review the SAE to determine if it is an expected SAE (i.e., whether or not the SAE is identified in nature, severity, and frequency in the Investigator Brochure).

